ID: IB2019-METABONE

Patterns of Care and Outcomes in Patients With Metastatic Bone Tumors (METABONE)

NCT03963531

Jan 5, 2007

INCLUSION

- Patients age > 12 year old at initial diagnosis
- Histology of Ewing's sarcoma type, osteosarcoma, chondrosarcoma
- Diagnostic of primary event between 2008 and 2018
- Diagnostic of unresectable locoregional disease where palliative treatment is indicated, or metastatic disease
- Treatment and monitoring made in one of the GSF-GETO centers, with follow up data on treatment received available.

OBJECTIFS

I. OBJECTIVES AND ENDPOINTS

The primary objective of the METABONE study is to give a retrospective descriptive analysis of clinico-biological profiles, patterns of care and modalities of treatment of patients with unresectable locally advanced and/or metastatic malignant bone tumors in a real-life national setting.

The primary endpoint is description of initial and local/metastatic relapse events management of adult patients with the diagnosis of Ewing's sarcoma, osteosarcoma, chondrosarcoma, made in one of the centers of the RESOS network between 2008 and 2018, in terms of therapeutic strategies including chemotherapy, surgery, radiotherapy, interventional radiology.

Secondary endpoints

- Description of systemic treatments received in the palliative setting in terms of **PFS** (progression free survival) and **TNT** (Time to next treatment)
- **Overall survival** from unresectable locally advanced and/or metastatic stage
- Identification of **factors associated with PFS and TNT** for molecules used in the unresectable locally advanced and metastatic setting
- Identification of **prognostic factors for overall survival** (OS) in the unresectable locally advanced and/ metastatic setting

II. METHODS

PATIENTS

We estimate the population size in the database of about 2800 patient cases.

We seek to include 800 patients to be screened in the present study.

We aim to get about 400 to 500 informative patients with unresectable locally advanced or metastatic disease.

VARIABLES

Variables collected will be those of the **CONTICABONE DICTIONNARY**

Descriptive data

Centers, number of patients per center

Initial patients characteristics at diagnostic: Age at diagnosis, gender, PS at diagnosis, previous history of specific disease (Li Fraumeni, Multiple Exostosis)

Tumor characteristics at diagnostic : location, side, size, multifocality, LR spread and type, stage N M, histology, grade, previous radiation area,

Initial treatment: surgery, type of surgery, margins, tumor spillage, residual cellularity, neo/adjuvant systemic treatment indication (start and stop date, type), radiation therapy, other treatment (cryotherapy, radiofrequency, embolisation), clinical trial inclusion

Metastatic relapse/event characteristics: PS, location of first metastasis, number of sites

Treatment of metastatic event: systemic treatment (PS molecule used, start and stop date, best RECIST response, date of progression, clinical trial), locoregional treatment (surgery, radiotherapy, cryotherapy, radiofrequency, embolisation), clinical trial.

Dates: Birth, initial diagnostic, surgery of primary, local relapse, metastatic relapse, start of each chemo line, date of progression for each chemo line, last contact, death

Samples: Molecular cytogenetics : method (RT PCR, FISH), transcript (FOR EWING SARCOMA ONLY)

Survival data

Median follow up

Progression free survival (PFS): PFS defined as the time from the systemic treatment onset to progression or death due to any cause, whichever comes first. When neither death nor progression is observed, PFS is censored at the date of last patient contact.

Time to next treatment (TNT): TNT defined as the time from the systemic treatment onset to the next treatment or death due to any cause, whichever comes first. When neither death nor new systemic therapy is observed, TNT is censored at the date of last patient contact.

Overall survival (OS): OS is defined as the interval between the diagnosis of first tumor event and the time of death. OS in the unresectable locally advanced setting is defined as the interval between the diagnosis of unresectable locally advanced setting (at diagnosis or relapse) and the time of death. OS in the metastatic setting is defined as the interval between the diagnosis of metastatic disease (at diagnosis or relapse) and the time of death. When death is not observed, OS is censored at the date of last patient contact.

STATISTICS

Statistical analysis of the baseline demographics and clinical outcomes will be based on all data available up to the cut-off date of August 31, 2021.

Descriptive statistics will be used to show the distribution of variables in the population.

The variables included in the univariate and multivariate analyses are the descriptive data including:

- type of chemotherapy used (poly vs mono, class of chemo: TKI, Ifosfamide, other)
- locoregional treatment of metastasis,
- inclusion in a clinical trial in first line,
- at least one inclusion in a clinical trial during metastatic stage,
- use of off-label drug at least once during metastatic stage

Multivariate logistic regression models will be used to identify biological and clinical factors associated with the type of treatment received after 1st line: in second, third, 4th line, and with the probability of survival 5 years after the diagnosis of metastases.

Follow-up times will be described as median values based on the inverse Kaplan–Meier estimator.

Prognostic factors of TNT for each line (1st, second, Third) and OS will be identified using Cox proportional hazard models.

The correlation between TNT and OS will be evaluated at each of the four first-lines of metastatic chemotherapy by a Spearman rank correlation coefficient and expressed as a value between 0 (no association) and 1 (perfect association). We will use a reviewed copula-based approach that introduces an iterative multiple imputation method for the estimation of the correlation coefficient. The data will be analyzed using the SAS v9.3 and R v3.3 software packages.

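### Selecting patients by date of primary diagnosis ties the diagnosis-to-advanced-disease interval to calendar time, and neither the interval nor calendar year is named as a model term

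*Combined protocol and SAP*

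**What the plan says.** The INCLUSION section sets two conditions that matter here. The first is a date window on the primary tumour: "Diagnostic of primary event between 2008 and 2018". The second is that advanced disease has been reached: "Diagnostic of unresectable locoregional disease where palliative treatment is indicated, or metastatic disease". This second event has no date window of its own. Under STATISTICS, the analysis is "based on all data available up to the cut-off date of August 31, 2021".

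The OS endpoint under Secondary endpoints runs "from unresectable locally advanced and/or metastatic stage". Under Survival data, metastatic OS is "the interval between the diagnosis of metastatic disease (at diagnosis or relapse) and the time of death", and PFS and TNT run from the start of a systemic treatment. One further definition in the same place starts earlier: "OS is defined as the interval between the diagnosis of first tumor event and the time of death".

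On covariates, STATISTICS says: "The variables included in the univariate and multivariate analyses are the descriptive data including". Five items follow, among them class of chemotherapy and trial inclusion, in first line and at any time in the metastatic stage. TNT by line and OS are to be modelled by Cox regression. The dates of initial diagnosis, local relapse and metastatic relapse are listed under Descriptive data. Nowhere is an interval between them, a synchronous/relapse indicator or a calendar-period term defined as a model variable. Truncation is not mentioned.

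**The concern.** A patient enters only if the advanced event falls before the cut-off, so the time available for a relapse to be seen depends on when the primary was diagnosed. Relapses after the cut-off are lost for recent diagnoses, and relapses during 2008-2018 from primaries diagnosed before 2008 are excluded altogether. Both edges of the diagnosis window link the interval to calendar time, for reasons that have nothing to do with the disease.

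The treatment factors to be tested plausibly change with calendar time as well. If the interval also carries prognosis, part of its effect will be read as an effect of drug class or trial inclusion. Identifying factors for PFS, TNT and OS is a stated secondary aim, so this bears on results the study intends to report.

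**Working it through.** The plan gives no power, event count or relapse-time figure, so there is nothing of its own to reproduce.

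**Inputs from the document:** diagnosis window 2008-2018, taken as January 1, 2008 to December 31, 2018; cut-off August 31, 2021.

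**Assumed, because the document gives no figure:** uniform diagnosis dates; exponential interval among eventual relapsers with median m of 18 to 36 months; 30% advanced at diagnosis where stated; hazard ratio for death of 1.0, 0.9 or 0.8 per year of interval.

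**1. Longest observable interval, W = cut-off minus diagnosis date (no assumption beyond the day and month).** January 1, 2008: 13.66 years. December 31, 2018: 2.67 years.

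**2. By year of diagnosis.** The share of eventual relapses falling after the cut-off is 2^(−W/m). For m = 2 years and an end-2018 diagnosis this is 2^(−2.67/2) = 39.7%; for January 2008 it is 2^(−13.66/2) = 0.9%. Two-year bands, by simulation:

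| Assumed median (months) | Captured, 2008-2009 | Captured, 2017-2018 | Median captured interval (months), 2008-2009 vs 2017-2018 |
|---|---|---|---|
| 18 | 99.7% | 80.9% | 17.8 vs 13.6 |
| 24 | 98.8% | 71.5% | 23.6 vs 15.4 |
| 36 | 94.6% | 56.8% | 33.3 vs 17.5 |

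**3. By year of the advanced event.** For an event a years after January 1, 2008, the interval must lie between max(0, a − 11) and a. An event at the end of 2008 thus has an interval of at most 1 year. One on August 31, 2021 has at least 2.67 years. From 2019 on, no event can be synchronous. Median interval among captured relapsers, by simulation:

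| Assumed median (months) | 2008-2009 events | 2017-2018 events | 2019-August 2021 events |
|---|---|---|---|
| 24 | 6.0 | 22.9 | 38.0 |
| 36 | 6.3 | 31.1 | 47.2 |

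With m = 24 months and 30% advanced at diagnosis, the synchronous share falls from about 61% of 2008-2009 events to 0% of 2019-2021 events. At the same m, the interval among relapsers correlates −0.20 with diagnosis year and +0.42 with event year. The two axes run in opposite directions.

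**4. Effect on a Cox model.** Simulations, 30% advanced at diagnosis, true hazard ratio 1.0 for the factor tested:

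- Era-linked treatment factor, m = 24 months: 0.94 without the interval when its effect is 0.9 per year, and 0.86 when it is 0.8; about 1.00 with the interval. These values depend on how sharply uptake changes. With uptake assumed to rise from 20% to 60% for events from 2015 on, a repeat gave about 0.96 and 0.92 without the interval.
- Diagnosis in 2015-2018 versus earlier, m = 36 months: 1.12 (0.9 per year) and 1.29 (0.8 per year) without the interval; 1.00 and 1.03 with it.
- Interval not prognostic (1.0 per year): no OS bias.

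**5. What a covariate leaves untouched.** With m = 36 months and 0.8 per year, unadjusted median OS is 2.09 years against 2.47 without truncation, and 5-year OS is 19.8% against 27.9%.

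**6. Cost of restricting to events within 2.5 years.** The share of captured relapsers dropped is (2^(−2.5/m) − q)/(1 − q), where q is the share missed over the whole window (5.7%, 10.2%, 19.6% for m = 1.5, 2, 3 years):

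- m = 1.5: (0.315 − 0.057)/0.943 = 27%
- m = 2: (0.420 − 0.102)/0.898 = 35%
- m = 3: (0.561 − 0.196)/0.804 = 45%

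**The case against.** A diagnosis-based cohort is a defensible choice: the primary endpoint covers management of both the initial disease and the relapses of patients diagnosed in 2008-2018. Patients advanced at diagnosis are eligible and lose nothing. With 30% of them and a 24-month median (both assumed), about 93% of the whole cohort is captured. Every bias figure rests on assumptions. All of this stands, and it limits the size of the point without removing the mechanism.

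Four stronger readings are tempting, and the document does not support them.

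- *Recently treated patients are selected for early relapse.* This holds by year of diagnosis. Chemotherapy class and trial inclusion for advanced disease follow the year of the advanced event, where later patients have longer intervals.
- *The interval is left out of the models.* The covariate list is open-ended, the dates stand among the descriptive data, and the data dictionary is not reproduced. One can say only that the interval is not named or defined.
- *Adding the interval would correct the problem.* It repairs the regression comparisons if correctly specified. It does not repair case mix, patterns of care or unadjusted survival curves, and the primary objective is descriptive.
- *Every outcome starts at advanced disease.* The general OS definition starts at the first tumour event.

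**Conclusion.** The concern holds in this narrower form. That the interval is tied to calendar time follows from the dates alone: the observable maximum falls from 13.66 to 2.67 years across diagnosis years, and synchronous disease cannot occur among events from 2019 on. It is also established that no interval or calendar-year term is named or defined.

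The size of the resulting bias is conditional. Under the assumptions shown, a treatment factor with no effect but with use that rises over time would show a hazard ratio of roughly 0.96 to 0.86. The direction is towards making later-era treatments look better, if longer intervals carry a better prognosis. There is no OS bias if the interval is not prognostic. This is a worthwhile correction to the secondary regression analyses and a limitation to state for the descriptive ones; it does not invalidate the cohort.

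**What to change.** In STATISTICS, add two derived terms to the PFS, TNT and advanced-stage OS models:

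- the interval from primary diagnosis to the advanced event, set to 0 if advanced at diagnosis, with a synchronous indicator or in preset bands. For unresectable locoregional disease, state which collected date marks the event;
- the calendar year of the advanced event. Diagnosis year should not be added as a third linear term, since it is event year minus interval.

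Report patterns of care and survival by interval band. State that these terms address the regression comparisons only, and give the truncation as a limitation of the descriptive and unadjusted results.

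An analysis limited to advanced events within 2.5 years of diagnosis may be shown as a check, since every patient diagnosed by the end of 2018 could complete that window. It makes diagnosis years comparable but not event years, describes early advanced disease only, and drops roughly 27% to 45% of captured relapsers under the assumed medians of 18 to 36 months. It should stay secondary.

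The cost is a few model parameters and one sensitivity analysis, using dates already listed for collection.

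### Entry requires treatment and treatment data at a network center, but OS starts earlier, so never-treated patients drop out and the treated share and OS are probably overstated

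*Combined protocol and SAP*

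**What the plan says.** The inclusion list has two criteria that matter here. One concerns disease: "Diagnostic of unresectable locoregional disease where palliative treatment is indicated, or metastatic disease". The other concerns place of care and data: "Treatment and monitoring made in one of the GSF-GETO centers, with follow up data on treatment received available". No minimum survival, follow-up time or number of treatment lines is set.

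The primary objective in section I concerns "patients with unresectable locally advanced and/or metastatic malignant bone tumors in a real-life national setting". The primary endpoint describes management "in terms of therapeutic strategies including chemotherapy, surgery, radiotherapy, interventional radiology". Neither this endpoint nor the treatment variables in section II include a category for patients managed without tumor treatment.

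The survival definitions in section II have different origins. For OS, "OS in the metastatic setting is defined as the interval between the diagnosis of metastatic disease (at diagnosis or relapse) and the time of death"; the unresectable setting is handled in the same way. For PFS, "PFS defined as the time from the systemic treatment onset to progression or death due to any cause, whichever comes first", and TNT has the same starting point. On loss to follow-up: "When death is not observed, OS is censored at the date of last patient contact".

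The plan contains no delayed-entry or landmark method, no count of exclusions with reasons, and no sensitivity analysis on this point.

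**The concern.** A patient with metastases enters the OS risk set, in principle, on the day they are diagnosed. Whether that patient is in the study depends on later events: receiving treatment at a center, and having data on it. A patient who dies before treatment, or for whom no tumor treatment is given, fails the criterion on its plain reading.

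Two results are exposed. The first is the primary description: if untreated patients cannot enter, the treated share is close to 100% by construction, and the study cannot say how often real-life care consisted of no tumor-directed treatment. The second is OS from the advanced stage, together with its prognostic models and the logistic model of 5-year survival after metastatic diagnosis. Patients who go untreated, or die before treatment can start, probably have short survival, so leaving them out raises the curve, most of all in the first months.

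**Working it through.** **What can be reproduced.** The plan states about 2800 cases in the database, 800 to be screened and 400 to 500 informative patients. 800/2800 = 28.6%, 400/800 = 50.0% and 500/800 = 62.5%. No exclusion rate, survival assumption or event count is given, so the targets cannot be derived and the bias cannot be computed from the documents.

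**Who is left out on the plain reading.**

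| Patient | Eligible? | Effect on OS |
|---|---|---|
| Treated at a center, dies soon after | Yes | None |
| Enters, later lost | Yes, censored at last contact | None from this criterion |
| Primary treated at a center, relapse untreated | Possibly; the text does not tie treatment to the advanced stage | None if admitted |
| Advanced at presentation, never treated | No | Upward if survival is short |
| Dies before any treatment | No | Upward |
| Treated, but treatment data missing | No | Direction unknown |

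**Illustration of size; all inputs are assumed.** Let f be the share left out, M the median OS of included patients (15 or 18 months) and m the median of those left out (2 or 3 months), with exponential survival. For everyone together,

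S(t) = (1 − f)·0.5^(t/M) + f·0.5^(t/m).

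The full-population median solves S(t) = 0.5, and the overstatement is M divided by that median, minus 1. Check for f = 0.10, M = 15, m = 3, t = 12.94: 0.90 × 0.5^(12.94/15) = 0.495 and 0.10 × 0.5^(12.94/3) = 0.005, which sum to 0.500. The overstatement is 15/12.94 − 1 = 15.9%.

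| f | Full median if 15 reported | Full median if 18 reported | Overstatement |
|---|---|---|---|
| 5% | 13.9–14.0 | 16.7 | 7–8% |
| 10% | 12.8–12.9 | 15.3–15.4 | 16–18% |
| 20% | 10.4–10.9 | 12.3–12.8 | 38–46% |

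At f = 10%, six-month survival would be reported as 75.8% against 69.5–70.7% (M = 15), or 79.4% against 72.7–73.9% (M = 18). Five-year survival moves less in absolute terms: with M = 18, 9.9% reported against 9.4%, 8.9% and 7.9% at the three values of f.

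**Dependence on prognosis.** If those left out live as long as the others (m = M), the bias is zero. If they live longer (m = 36, M = 18), the full median is 18.6, 19.1 or 20.4 months, and the reported 18 is too low.

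**Treated share.** If everyone left out is untreated, the study shows 100% against 95%, 90% or 80%. The number left out is n·f/(1 − f): 21, 44 or 100 behind 400 included patients, and 26, 56 or 125 behind 500.

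**The case against.** The strongest reply is that the criterion may only fix where care took place and that a record exists. It does not say the treatment must be for advanced disease, and the primary endpoint covers initial management as well as relapse. A patient treated for the primary at a center and untreated at relapse could therefore qualify. This stands. It narrows the group at risk to mainly those advanced at presentation, but does not remove it, and it would mean that untreated patients are filtered differently at presentation and at relapse.

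A reader might infer more than the documents support:

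- *That all early deaths and all lost patients are removed.* No minimum survival is set, and patients lost after entry are censored.
- *That the step from 800 screened is a second filter of the same kind.* The text reads "We aim to get about 400 to 500 informative patients with unresectable locally advanced or metastatic disease", which ties the reduction to disease stage. The word for usable patients is undefined, but nothing links it to survival or follow-up.
- *That every excluded group biases OS upward.* For patients missing only treatment files the direction depends on their prognosis, which is not given.
- *That late referral inflates OS by a known amount.* A patient referred alive after the advanced diagnosis is credited with the time before referral, but no referral frequency is stated. The primary endpoint also refers to diagnosis within the network, which limits this scenario at least for the initial diagnosis.
- *That the effect of performance status is attenuated.* This is plausible if poor status leads to non-treatment, but the documents offer nothing to quantify it.

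It is also fair that PFS, TNT, the models of treatment after first line and the TNT–OS correlation concern treated patients, and that the untreated proportion is not a listed endpoint. Even so, a description of real-life care that cannot contain untreated patients is limited in what it can claim.

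**Conclusion.** The point holds in a limited form. Followed as written, the criterion selects on events after the OS origin, and nothing in the plan compensates. This is a rule that biases results, not merely a missing detail. The treated share and OS from the advanced stage are likely overstated through the loss of never-treated patients and deaths before treatment.

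The size is unknown. The 7–8%, 16–18% and 38–46% overstatements of median OS rest entirely on an assumed excluded share (5%, 10%, 20%), assumed medians and exponential survival. The upward direction rests on the excluded patients having shorter survival. That is reasonable for untreated patients and deaths before treatment, but not established for missing files. A general claim that the study's patterns of care and all its time-to-event results are biased upward would go too far.

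**What to change.** - Reword the criterion so that a patient with a dated unresectable or metastatic diagnosis, managed at a network center and with vital status and date of last contact, is eligible whether or not tumor treatment was given.
- Code no tumor-directed treatment and treatment unknown as separate categories in the primary description, and keep these patients in OS.
- Report the numbers screened and excluded, with reasons.
- Where a first-visit date can be retrieved, add an OS sensitivity analysis with delayed entry: patients referred after the advanced diagnosis join the risk set at their first visit.

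The cost is modest for a retrospective database study. Dates of metastatic relapse, last contact and death are already on the list of collected dates. A first-visit date is not among them and would have to be added. The sponsor should expect more missing treatment detail and a probably lower OS figure. If the rewording is not feasible, the plan should at least state whether untreated patients are eligible, report exclusions, and confine the OS and treated-share conclusions to the population actually selected.

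### Locoregional treatment of metastases is a planned covariate in analyses that model TNT line by line, but the listed variables give it no date or line number, so it can enter only as an undated flag subject to immortal-time bias

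*Combined protocol and SAP*

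**What the plan says.** All references are to the combined protocol and SAP.

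- **II. METHODS, Variables, treatment of the metastatic event.** Systemic treatment is recorded with timing: "systemic treatment (PS molecule used, start and stop date, best RECIST response, date of progression, clinical trial". Local procedures are recorded by type only: "locoregional treatment (surgery, radiotherapy, cryotherapy, radiofrequency, embolisation), clinical trial".
- **Variables, Dates.** After birth and initial diagnosis, the list continues "surgery of primary, local relapse, metastatic relapse, start of each chemo line, date of progression for each chemo line, last contact, death". The only procedure dated is surgery of the primary.
- **Variables, opening line.** "Variables collected will be those of the CONTICABONE DICTIONNARY". That dictionary is not reproduced.
- **Statistics.** The covariates for the univariate and multivariate analyses include "locoregional treatment of metastasis", with no coding or timing rule. Cox models are planned for TNT in each of lines 1 to 3 and for OS. No model is named for PFS, and neither time-dependent covariates nor a landmark is mentioned.
- **Survival data.** "PFS defined as the time from the systemic treatment onset to progression or death due to any cause, whichever comes first". For TNT: "TNT defined as the time from the systemic treatment onset to the next treatment or death due to any cause, whichever comes first". The TNT censoring sentence that follows refers only to a new systemic therapy.
- **I. Objectives and endpoints.** PFS and TNT of systemic treatments in the palliative setting, and the factors associated with them by molecule, are secondary endpoints.

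**The concern.** Each line's clock starts at the onset of systemic treatment. A procedure on metastases during that line happens later, and only in patients whose line has lasted long enough to reach it. Coding such patients as treated from time zero credits the procedure with a period in which, by construction, they could not have had the event. That is immortal-time bias.

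Without a date or line number there is a second error. A patient whose metastases are resected during line 1 and a patient irradiated after line 3 carry the same code, and a procedure done after line 3 can appear as a predictor of line 1 TNT.

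At stake is a published prognostic factor, and possibly an apparent benefit of local treatment, that the coding alone could create. Because the flag is correlated with the drug when uptake differs between regimens, the drug contrasts in the same model are distorted too.

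**Working it through.** The plan states no power, effect size or uptake of procedures, so there is no figure of its own to reproduce. Every input below is an assumption, chosen to show direction and rough size.

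**1. Where the immortal time comes from.** Assume exponential times with median 6 months, two equally active drugs A and B, and a procedure at month 3 in 40% (A) or 10% (B) of lines still running. No procedures fall outside the line.

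- Hazard: ln 2 / 6 = 0.1155 per month. Share still on the line at month 3: exp(−0.1155 × 3) = 0.707, so 29.3% have ended, equally for A and B.
- Flagged in A: 0.40 × 0.707 = 28.3%; unflagged 71.7%. All early events fall among the unflagged: 29.3 / 71.7 = 40.8% have ended by month 3.
- Flagged in B: 0.10 × 0.707 = 7.1%; unflagged 92.9%. Early events among the unflagged: 29.3 / 92.9 = 31.5%.
- Early events among the flagged: 0% in both groups.

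So the flag looks protective even if the procedure does nothing. Among the unflagged, A looks worse than B (40.8% against 31.5%) although the drugs are equal.

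**2. What a Cox model returns in that scenario (simulation).**

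| Quantity | Procedure has no effect | Procedure halves the later hazard |
|---|---|---|
| Drug HR, unadjusted (truth 1.0) | 1.0 | 0.85 to 0.87 |
| Drug HR, with undated flag (truth 1.0) | about 1.1 | about 1.1 |
| HR of the flag itself | about 0.67 (truth 1.0) | 0.37 to 0.38 (truth 0.5) |

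With uptake of 30% against 10% and the later hazard halved, the unadjusted drug HR is 0.90 to 0.91 and the flag moves it to 1.07 to 1.08.

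**3. Different inputs, including later-line procedures.** 450 patients, median 4 months, procedure at a uniform time in months 0 to 3, planned in 30%/30% or 50%/20% of the two drug groups, and 20% with a procedure in a later line; 40 replicates.

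| True HR of procedure | Undated flag, 30/30 and 50/20 | Dated, time-dependent, 30/30 and 50/20 |
|---|---|---|
| 1.0 | 0.83 and 0.79 | 0.99 and 1.00 |
| 0.8 | 0.73 and 0.69 | 0.79 and 0.80 |
| 0.6 | 0.62 and 0.61 | 0.59 and 0.62 |

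The drug HR (truth 1.0) was 0.96 to 1.06 with the flag and 0.97 to 1.02 with dated coding. In the last row the flag is nearly right, because procedures from other lines dilute it towards 1 while immortal time pulls it down. That offset is accidental and cannot be relied on.

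**4. Unadjusted description per molecule.** With a share p of lines still running at month 3 having the procedure, and the hazard halved afterwards, the pooled survival for t > 3 is

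S(t) = (1 − p)·exp(−λt) + p·exp(−3λ − λ(t − 3)/2), λ = 0.1155.

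Putting y = exp(−λt/2) and S = 0.5 gives (1 − p)y² + 0.841p·y − 0.5 = 0.

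- p = 0.1: y = 0.700, t = 6.17 months, 3% above 6.
- p = 0.4: y = 0.675, t = 6.81 months, 14% above 6.

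**5. TNT wording.** The figures above treat the procedure as something that happens during the interval. Read literally, the TNT event is any next treatment, so a procedure could end TNT. Its date would then be needed to calculate TNT at all. The censoring sentence points to the other reading.

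**The case against.** **The dictionary may hold the dates.** This stands in part. The Variables section is a summary of a source the reader cannot see, so the absence is shown only for the listed fields. But the plan itemises its dates, leaves these out and gives no timing rule. Even if the dates exist, nothing tells the analyst to use them.

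**The plan adjusts for local treatment, so its effect is not credited to the drug.** This is right as far as it goes. A reader might infer that drug results throughout the study absorb the effect of procedures. The documents do not support that: the covariate is planned, and in the illustration with no procedures outside the line the flag pushes the drug HR above 1, the opposite direction. False credit to a drug is possible only in results not adjusted for the procedure, that is the descriptive PFS and TNT per molecule, univariate contrasts, and PFS, for which no model is named. For a contrast between drugs it needs both a real procedure effect and unequal uptake. With equal uptake in the second simulation the unadjusted drug HR was 0.97 to 0.99.

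**The study is mainly descriptive.** True of the primary objective, and no formal drug comparison is stated. But factors for PFS and TNT by molecule are secondary endpoints, and the Cox models for TNT are planned explicitly.

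**Conclusion.** The concern holds in this limited form: as listed, the data support only an undated flag, and using it in the TNT models for lines 1 to 3 gives a biased locoregional term and can disturb the drug terms. Across the two sets of assumptions, a procedure with no effect would show an HR of about 0.67 to 0.83. The size depends on the timing of procedures, on uptake and on how many fall in other lines, none of which the documents give.

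The possible inflation of unadjusted medians is the lesser part: 3% to 14% under the month-3 assumption. A larger figure can be obtained by giving the treated lines a median of 18 instead of 6 months from day 0 (9% to 48% at 10% to 40% uptake). That contradicts the premise that procedures take place during the line, and should not be used. Nor do the documents say that procedures prolong PFS or TNT, or that fitter patients receive them more often; both are conditions here, not findings.

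**What to change.** 1. Check whether the CONTICABONE dictionary records the date of each locoregional treatment of metastases. If not, add one date per procedure.
2. In each line-specific model, code procedures before line start as a baseline covariate and procedures during the line as a time-dependent covariate, or use a landmark analysis.
3. Report PFS and TNT per molecule for all lines and, descriptively, by whether a procedure took place during the line. State that this split is itself subject to immortal time unless landmarked.
4. Reconcile the TNT event and censoring sentences so that it is clear whether a locoregional procedure ends TNT. If it does, a procedure during the line is an outcome of that model and not a covariate in it.
5. If dates cannot be retrieved, remove the variable from the line-specific TNT models and report it descriptively only.

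Cost: SAP wording alone if the dates already exist. Otherwise modest extra chart abstraction for the targeted 400 to 500 informative patients; with diagnoses going back to 2008, some dates may be missing, and their number should be reported.
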